Demographic/Medical History/Insurance Variables/Personal Experience/Media Exposure: will be assessed using the form in **Appendix F**. Questions will assess age, race, education, and marital status. These items have been used for descriptive reporting in our previous research without interpretation or scoring difficulties. In the proposed study, questions about personal experience will relate to previous information about mammography screening experiences or to information gathered during the grant period. Women will also be asked about experiences with close friends or relatives with cancer. Participants will be queried regarding any CRC or BC screening recommendations or counseling outside of the study protocol. *Women will also be queried about out-of-pocket cost for any BC and CRC screening.* Cost-effectiveness will be measured and calculated as described under the Data Analysis section.

Overall Functioning: will be assessed using the Medical Outcomes Study - Short Form 12 (SF-12[®]), a 12-item scale that yields summary physical and mental health outcome scores that are interchangeable with those from the SF-36[®]. The SF-12[®], published in early 1995, is one of the most widely used instruments that reproduces the SF-36[®] physical and mental health summary scales (PCS and MCS) as well as the eight subscales of the original SF-36. Reliability and validity have been well supported; test-retest reliabilities of 0.89 and Cronbach alphas of 0.76 are reported.⁽¹⁴⁰⁾

Cost-effectiveness will be measured and calculated as described under the *Data Analysis* section.

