Hypothesis 1- Efficacy Analysis: Similar to the approach in Hypothesis 1 for **Group A**, screening adherence across the four randomized arms will be tested initially with the chi-square test for a 2x4 cross-classification table and then adjusting for covariates in logistic regression models. However, the statistical procedures will be generalized versions (Mantel chi-square and ordinal logistic regression) to accommodate an ordinal outcome. The three possible ordinal responses for the outcome are: 1) no adherence, 2) adherence to either CRC or BC screening, and 3) adherence to both CRC and BC screening. Specifically, we will perform: a) the Mantel chi-square test of linear trend and the Liu-Agresti ordinal odds ratio (the latter is a contingency-table-based statistic but assumes proportional odds) on a 2 x 3 cross-classification table (intervention group by ordinal adherence), and b) ordinal, instead of binary, logistic regression models. If the assumption of proportional odds is not satisfied, a more general logistic regression model, the generalized logit model, will be employed, and two odds ratios, instead of a single Liu-Agresti odds ratio, will be reported for the classification tables. Analyses of stage will be the same as for adherence, except the three possible ordinal responses would be based on improvement (from baseline) in stage of adoption: 1) no improvement in stage, 2) improvement in stage of either CRC or BC screening, and 3) improvement in stage of both CRC and BC screening. The Preliminary Studies show we have a great deal of experience analyzing outcomes of screening adherence and stage improvement, for both BC and CRC outcomes.

Aim 2: Analyses for cost effectiveness is described next. To conduct cost-effectiveness (CE) analysis of a cancer screening program, it is necessary to determine both the effectiveness of a given intervention (as measured by the achieved outcomes) and the costs of providing the intervention to both groups A and B. The cost-effectiveness analysis will be conducted from the perspective of both the provider and the participants.

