Program Effectiveness: The main effect is screening compliance at 6 months from the baseline measure as determined by the randomized trial. For those in **Group A**, CRC screening is the outcome. For **Group B**, there are three outcome groups: CRC screening adherence, BC screening adherence, and adherence to CRC and BC screening. Outcomes will be determined with an “intent-to-treat” analysis by analyzing data from all women who originally consented and were randomly assigned to a research arm regardless of deviations from the protocol, the degree of treatment they received (e.g., regardless of whether TIWeb was viewed or CSC was made), or withdrawal from treatment or loss to follow-up. The use of claims data and medical records data for the main outcome of adherence will make it possible to analyze adherence at 6 months even for women who dropped out, as long as claims data for those women can be obtained.

Program Costs: To calculate the costs of the interventions, we will consider delivery costs only. Costs associated with research and development (R&D) activity or costs of screening tests are excluded. The cost of developing the TIWeb is expected to be a major pre-intervention R&D cost. Researchers have debated how to handle these “first-copy” costs and there is no universally accepted “correct” answer. First-copy costs, defined as costs incurred in establishing a regimen or intervention, are considered quasi-fixed costs independent of the number of units produced, once production is started. Generally, first-copy costs are excluded when they involve situations in which much of the intervention is already in existence and only modification is needed to adapt it for implementation. While R&D costs can be high, they are “sunk cost” from a societal perspective, in any future decision to implement the interventions. The final product developed for this study could be made available to

other organizations. We expect managed care organizations would not develop their own TIWeb, but would rely on public access or licensing arrangements to secure such educational material. However, the cost of developing the TIWeb will be calculated to inform future developers of the approximate cost of developing this type of interactive technology for health promotion interventions and to test CE analysis with and without these costs.

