The total costs of an intervention include both direct and indirect costs. Direct costs are those directly related to services provided to the participants and include such inputs as personnel time, supplies, postage, and capital equipment. The total cost of a specific intervention will be based on several inputs including: the cost of personnel (time needed to provide the intervention multiplied by the salary and benefit cost); the cost of nondurable, consumable supplies (quantity consumed times the unit price); and the cost of durable capital equipment (depreciated over the expected life of the asset, to reflect annual costs). Postage will be a non-trivial cost in this study since some of the correspondence with participants will be by mail. Ancillary miscellaneous costs (printing, workstation design, space rental, phone charges, etc.) will be obtained from the project's monthly expenditures. Incentives used in this study to secure cooperation of the participants will not be considered a cost of the intervention since these are considered research costs and not a necessary ingredient of the interventions. Incentives are provided for data collection and not for participation in an intervention. Overhead costs, including housekeeping, administration costs, rent, building and equipment depreciation, insurance expenses, and utilities are very difficult to allocate to the appropriate intervention without developing a detailed accounting procedure, which is beyond the scope of this project. Therefore, overhead costs will be estimated by a percent of direct cost, based on previous health promotion studies. The base case indirect cost rate will be 30 percent of direct cost.⁽¹⁴²⁾ Participant time costs (the time a woman spends participating in the intervention) will be included in the cost figures since participant time has value from a societal perspective. Participant time will be valued by the national median wage rate (<http://www.bls.gov/bls/blswage.htm>) Participant time cost will be excluded when computing costs from the provider perspective.

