Bundling screening promotion services to promote multiple screening tests for women in group B presents a special cost problem due to the difficulty of allocating cost to specific outcomes. The main difference in cost between participants in **Group A** and those in **Group B** will be participant time and telephone counseling time required to communicate information about two versus one type of screening. These costs will be directly allocated to the screening interventions by tracking time for each participant. Other implementation costs will be the same for subjects eligible for either one test or two screening tests (e.g., recruitment). For group B, we follow methods employed by Chirikos et al. (2004)⁽¹⁴³⁾ to adjust the cost estimate for subjects eligible for two screening tests. In their study of an office-based primary care tracking system to increase screening for breast, cervical, and colorectal cancer, they apportioned the cost to subjects based on the number of tests they were eligible for. If a participant was eligible for two screening tests, they were assigned ½ of the intervention cost and the full intervention cost if they were eligible for only one test. Thus, cost for participants in group B will consist of directly allocated cost for their time and nurse counselor time and other costs apportioned by the number of tests for which they are eligible (see equations below).

Cost-effectiveness Analysis: The cost-effectiveness evaluation is examined from the societal perspective and from the more limited perspective of the provider to inform future decision-makers about the relative efficiency of the alternative interventions. The analysis focuses on the incremental cost per additional individual who is adherent (i.e., has a CRC, BC, or both screening tests during the observation period) for each alternative intervention. The intervention costs will include participant time costs and resource costs and be

valued in 2010 constant U.S. dollars. This focus is consistent with the recommendations of the Report of the Expert Panel on Cost-Effectiveness in Health and Medicine.⁽¹⁴⁴⁾ The base case will be defined as the estimate of costs and effects derived from the best point estimate of intervention parameters. Planning, implementation, and participant costs will be tracked for the interventions.

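### The Aim 2 cost-effectiveness analysis is labelled societal, but it leaves out screening-test costs and plans no run that includes them

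*Combined protocol and SAP*

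**What the plan says.** All of this is in D.13, Aim 2, unless another section is named.

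- **Perspective, opening paragraph:** "The cost-effectiveness analysis will be conducted from the perspective of both the provider and the participants".
- **Perspective, Cost-effectiveness Analysis:** "The cost-effectiveness evaluation is examined from the societal perspective and from the more limited perspective of the provider".
- **Scope, Program Costs:** "To calculate the costs of the interventions, we will consider delivery costs only". The next sentence reads: "Costs associated with research and development (R&D) activity or costs of screening tests are excluded".
- **Participant time, Program Costs:** "Participant time costs (the time a woman spends participating in the intervention) will be included in the cost figures". Then: "Participant time cost will be excluded when computing costs from the provider perspective". No other item is named as separating the two perspectives.
- **Out-of-pocket payments, D.11:** "Women will also be queried about out-of-pocket cost for any BC and CRC screening". D.13 uses them as a covariate in the Aim 1 models and as a possible effect modifier in Aim 3. They are not among the listed costs.
- **ICER equations:** each divides a cost difference by a difference in the percentage screened, stepping from usual care to TIWeb, to CSC, to both. No term depends on which CRC test was done.
- **Sensitivity analyses:** staff wages and overhead rates are the examples given. A comparison with and without is promised for the cost of developing the website, but not for test costs.

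**The concern.** A societal analysis should count the resources that an intervention sets in motion, whoever pays. Here the main downstream resource is the screening test, and its total cost rises with every additional woman screened. A participant perspective should at least cover what the woman spends, in time and money, to be tested. The plan counts neither.

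A second issue concerns CRC screening. An average-risk woman may choose FOBT or colonoscopy (D.8), and either one places her in the action stage (Table 6). The two therefore count as the same effect, and the price of the test is left out for both. If one delivery mode leads to more colonoscopies and another to more mailed kits, the ICERs cannot show it.

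B.8 presents the results as guidance for decision-makers choosing between interventions. A reader who takes the label at face value would think that test costs had been weighed.

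**Working it through.** **1. Does the label match the costs?**

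| Cost item | In the ICER? | Source |
|---|---|---|
| Staff time, supplies, postage, equipment, overhead | Yes | Program Costs |
| Woman's time in the intervention | Yes, except in the provider version | Program Costs |
| Screening tests | No, excluded explicitly | Program Costs |
| Woman's time for the test | Not listed | Program Costs defines participant time as intervention time |
| Out-of-pocket payment for the test | Not listed | Collected under D.11, used only as covariate and moderator |

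The supposed societal version is thus the provider version plus intervention time. It is not societal, and it is not a full participant perspective.

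**2. What does the omission do to a CRC ICER?**

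The plan states no ICER, unit price or test mix, so there is no figure of its own to reproduce. Let p be CRC adherence, m the share of adherent women whose test was colonoscopy, and C and F the unit costs of colonoscopy and FOBT. Assume one CRC test per adherent woman. For arm b against arm a, the test cost left out per additional adherent woman is

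[p_b(m_b·C + (1 − m_b)·F) − p_a(m_a·C + (1 − m_a)·F)] / (p_b − p_a).

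Inputs: the D.12 table plans 6-month CRC adherence of 20%, 30%, 40% and 55% for usual care, the tailored program (headed TIDVD there, read here as TIWeb), CSC and both. These rates are for Groups A and B combined. Using them for group-specific ICERs is an assumption. So are all colonoscopy shares.

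*Equal mix.* If m is the same in both arms, the expression reduces to m·C + (1 − m)·F whatever the adherence rates. At m = 50% every CRC ICER omits 0.5C + 0.5F, and the order of the CRC ICERs is unchanged.

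*Unequal mix, CSC against TIWeb (40% v 30%), TIWeb share 50%:*

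| CSC colonoscopy share | Colonoscopies omitted per additional adherent woman | FOBTs omitted |
|---|---|---|
| 30% | (0.40×0.30 − 0.30×0.50)/0.10 = −0.3 | (0.40×0.70 − 0.30×0.50)/0.10 = 1.3 |
| 40% | (0.16 − 0.15)/0.10 = 0.1 | (0.24 − 0.15)/0.10 = 0.9 |
| 50% | (0.20 − 0.15)/0.10 = 0.5 | (0.20 − 0.15)/0.10 = 0.5 |
| 60% | (0.24 − 0.15)/0.10 = 0.9 | (0.16 − 0.15)/0.10 = 0.1 |
| 70% | (0.28 − 0.15)/0.10 = 1.3 | (0.12 − 0.15)/0.10 = −0.3 |

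Each 10-point change in the CSC share moves the omitted cost by 0.4(C − F). The other two steps behave alike. With a 50% share in the comparator and 60% in the more intensive arm, TIWeb against usual care omits (0.18 − 0.10)/0.10 = 0.8 colonoscopies, and both against CSC omits (0.33 − 0.20)/0.15 = 0.87.

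**3. Can the mix differ by arm?**

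Yes, but nothing shows that it will. Both modes present average-risk women with the same choice (D.8). The route to the test differs (D.7): in the CSC the nurse offers a kit or an appointment at the end of the call, while a TIWeb participant has to phone a dedicated number herself. The documents give no direction or size for any resulting difference.

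**4. Which ICERs are touched?**

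The mix matters for ICERs with CRC screening in the effect measure. As printed, the Group A equations use the percentage screened for breast cancer, although Program Effectiveness makes CRC screening the Group A outcome. Until that is corrected, the mix affects only the Group B CRC and joint ICERs.

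**The case against.** The strongest reply is that the narrow scope is declared. B.8 defines the measure as cost per individual screened, Program Costs says that only delivery is costed, and the stated purpose is to compare the efficiency of running the interventions. The item that separates the two perspectives is named. This stands: a careful reader can see what is counted, and the delivery-cost ICER is a valid quantity. It does not rescue the label, because the same section still calls the evaluation societal.

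The wage and overhead items are only examples, so a run with test costs is not ruled out. But none is specified, whereas a with-and-without run is specified for development cost.

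A reader might go further and infer that the omission is worth a known sum, or that the ranking of the arms would reverse under true societal cost. The documents support neither. They contain no unit prices and no expected test mix. With equal mix the order of the CRC ICERs does not change, and whether an unequal mix would change it depends on prices and delivery costs that are not given. Nor is it settled that every test enters at zero cost, since a mailed FOBT kit could be counted among the supplies.

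**Conclusion.** The concern holds as a matter of labelling and of a missing sensitivity analysis. The plan claims a perspective that its list of costs does not deliver, and it describes that perspective in two ways. Leaving out test costs shifts the CRC ICERs by one constant if the FOBT/colonoscopy mix is equal across arms, and by unequal amounts if it is not. In the CSC against TIWeb comparison, a 10-point difference in colonoscopy share in either direction moves the omitted colonoscopies per additional adherent woman from 0.5 to 0.9 or to 0.1. This rests on the planned adherence rates, an assumed 50% share in TIWeb and one test per adherent woman. It shows how sensitive the ICER is to the mix and does not predict the mix. No dollar amount and no reversal of ranking is established. Only Aim 2 is affected; the efficacy analysis of Aim 1 is untouched.

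**What to change.** 1. **Relabel.** In the opening of Aim 2, the participant-time text in Program Costs, and Cost-effectiveness Analysis, use the same two names: provider delivery cost, and provider delivery cost plus participant intervention time. Draw no societal conclusion from the base case.
2. **Report CRC test type by arm.** Use claims together with the chart audit that D.11 already plans for FOBT. Claims alone would miss some FOBTs and distort the mix.
3. **Pre-specify one sensitivity ICER for the CRC outcomes** that adds test cost by type, at stated unit prices with a range. Do not add out-of-pocket payments to a full test price, because the woman's share would be counted twice. Use them only in a separate participant-perspective figure, and only if they are collected for tests done during the trial. D.11 describes them with the demographic items, which Table 7 schedules at baseline only.
4. **Say whether mailed FOBT kits are excluded tests or included supplies,** so that no kit is costed twice.

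The cost is some rewording and a small extra analysis on data largely planned already, plus a source for unit prices. The sensitivity ICER will probably look less favourable than the base case. It will also still count one FOBT and one colonoscopy as the same unit of effect, although B.2 gives them different screening intervals (yearly and every 10 years). That limit should be stated when it is reported.

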An important component of this proposal is the estimation of the efficacy and cost-effectiveness of interactive interventions tailored to beliefs and stage of adoption alone and together. Similar to other studies, the outcome to be compared in the cost-effectiveness analysis is the proportion of participants in each of the intervention arms who have had recommended CRC or BC screening tests during the six-month period following initial intervention. Using this design, we will be able to determine if aTIWeb, a CSC, or a TIWeb+ CSC will significantly increase adherence for CRC and/or BC screening and at what costs. If efficacy and cost effectiveness relative to other interventions are demonstrated with the TIWeb program, it could be promoted at health care visits. If the CSC increases screening at an acceptable incremental cost when added to the TIWeb, office staff could make telephone counseling calls to participants from the health care setting after the TIWeb.

B.9. Researchers have tested the effectiveness of intervening simultaneously for multiple health behaviors. In 2005, Emmons et al. reported that a telephone-delivered intervention which focused on six behavioral risk variables for colorectal cancer was effective in promoting change.⁽¹⁰²⁾ In a different research study, a home-based intervention to change smoking, high fat diet, and sun exposure produced significant changes as compared to a control.⁽¹⁰³⁾ Recently, a series of articles addressed multiple behavior research.⁽⁵⁾ Behaviors included weight management, smoking, exercise, and fruit and vegetable intake.⁽¹⁰⁴⁻¹⁰⁶⁾ All interventions that addressed multiple behavior change were effective.

[figure not shown]

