The primary cost-effectiveness measures will be the incremental cost-effectiveness ratios (ICERs) obtained by dividing the additional per target individual cost by the additional percent of target individuals who are screened by the end of the follow-up period, comparing the control group to the TIWeb group, to the CSC group, to the TIWeb+CSC group moving from the least resource-intensive to the most resource-intensive interventions (equations 1,2,3). These measures will be based on intention to treat methods and correspond to the observation period of the study.⁽¹⁴⁵⁾

Group A (cost fully allocated to BCS intervention)

- 1) $ICER_1 = (Cost_{TIWeb} - Cost_{UC}) \div (\%BCS_{TIWeb} - \%BCS_{UC})$
- 2) $ICER_2 = (Cost_{CSC} - Cost_{TIWeb}) \div (\%BCS_{CSC} - \%BCS_{TIWeb})$
- 3) $ICER_3 = (Cost_{TIWeb+CSC} - Cost_{CSC}) \div (\%BCS_{TIWeb+CSC} - \%BCS_{CSC})$

Group B (cost adjusted for joint production)

BCS: (directly allocated plus 1/2 of non directly allocated cost applied to BCS intervention)

- 1) $ICER_1 = (Cost_{TIWeb} - Cost_{UC}) \div (\%BCS_{TIWeb} - \%BCS_{UC})$
- 2) $ICER_2 = (Cost_{CSC} - Cost_{TIWeb}) \div (\%BCS_{CSC} - \%BCS_{TIWeb})$
- 3) $ICER_3 = (Cost_{TIWeb+CSC} - Cost_{CSC}) \div (\%BCS_{TIWeb+CSC} - \%BCS_{CSC})$

CRC: (directly allocated plus 1/2 of non directly allocated cost assigned to CRCS intervention)

- 1) $ICER_1 = (Cost_{TIWeb} - Cost_{UC}) \div (\%CRCS_{TIWeb} - \%CRCS_{UC})$
- 2) $ICER_2 = (Cost_{CSC} - Cost_{TIWeb}) \div (\%CRCS_{CSC} - \%CRCS_{TIWeb})$
- 3) $ICER_3 = (Cost_{TIWeb+CSC} - Cost_{CSC}) \div (\%CRCS_{TIWeb+CSC} - \%CRCS_{CSC})$

BCS & CRCS: (all costs allocated to joint BCS & CRCS intervention)

- 1) $ICER_1 = (Cost_{TIWeb} - Cost_{UC}) \div (\%BCS \& CRCS_{TIWeb} - \%BCS \& CRCS_{UC})$
- 2) $ICER_2 = (Cost_{CSC} - Cost_{TIWeb}) \div (\%BCS \& CRCS_{CSC} - \%BCS \& CRCS_{TIWeb})$
- 3) $ICER_3 = (Cost_{TIWeb+CSC} - Cost_{CSC}) \div (\%BCS \& CRCS_{TIWeb+CSC} - \%BCS \& CRCS_{CSC})$

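### For Group B, no cost-effectiveness ratio sets the full cost against all the screening gained, and the measure the text appears to state has no equation

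*Combined protocol and SAP*

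**What the plan says.** Section B.8 gives the outcome for the cost-effectiveness comparison as "the proportion of participants in each of the intervention arms who have had recommended CRC or BC screening tests during the six-month period" after the intervention. Section D.13, Aim 2, Cost-effectiveness Analysis, puts the focus on the "incremental cost per additional individual who is adherent (i.e., has a CRC, BC, or both screening tests during the observation period". The paragraph that introduces the ratios divides by "the additional percent of target individuals who are screened by the end of the follow-up period", without saying which test.

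The Program Effectiveness paragraph of the same section says that for Group B "there are three outcome groups: CRC screening adherence, BC screening adherence, and adherence to CRC and BC screening". The equations follow that list, with three sets for Group B:

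- "BCS: (directly allocated plus 1/2 of non directly allocated cost applied to BCS intervention", over the difference in percent with breast screening;
- "CRC: (directly allocated plus 1/2 of non directly allocated cost assigned to CRCS intervention", over the difference in percent with CRC screening;
- "BCS & CRCS: (all costs allocated to joint BCS & CRCS intervention", over the difference in percent with both.

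The costs allocated directly are each woman's own time and the counselor's time, tracked per participant. Other costs are divided by the number of tests for which she is eligible. The Aim 1 efficacy analysis for Group B uses an ordinal outcome (neither, either, both), so it gives credit for one test.

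**The concern.** Section B.8 and the focus sentence in D.13 appear to describe one effect measure: a woman counts once if she has had a CRC test, a breast test or both. No Group B equation has that denominator.

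The equations that do exist leave a gap whichever way that sentence is read. In the full-cost set, a woman moved from no test to one adds cost and nothing to the denominator, although Aim 1 scores her as a partial success. The single-test sets credit her, but against part of the cost, and the one-half share depends on the tests she needed and not on the tests the intervention produced.

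Aim 2 compares four conditions, and the trial's rationale is that promoting both tests together is more efficient. With three sets of ratios for Group B and none named as decisive, the answer can depend on which set is read.

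**Working it through.** The protocol states no ratio, arm cost or joint screening rate that could be reproduced. The check is whether the choice of denominator can matter at rates taken from the protocol.

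**Inputs**

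- CRC adherence at 6 months: 20% usual care, 30% website (labelled TIDVD in the table), 40% call. Source: D.12 table, for Groups A and B combined; using it for Group B is an assumption. As a check that the rates are read correctly, power at 357 per arm recomputes to 0.871, 0.801 and 0.981 for pairs 1v2, 2v3 and 3v4, against the stated .87, .80 and .98.
- Mammography at 6 months: 45% usual care, 61% DVD, 56% phone. Source: section C, a study of women nonadherent to breast screening; using it for Group B is an assumption.
- Association between the two tests: the Specific Aims call the behaviors correlated but give no size. Assumed: correlation 0, 0.3 and 0.5 in a bivariate normal threshold model.

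**Formulas.** P(both) comes from the model. P(at least one) = P(CRC) + P(BC) - P(both). Tests per 100 women = 100 × [P(CRC) + P(BC)].

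| Correlation | Both, % (usual care / website / call) | At least one, % (usual care / website / call) |
|---|---|---|
| 0 | 9.0 / 18.3 / 22.4 | 56.0 / 72.7 / 73.6 |
| 0.3 | 12.4 / 22.2 / 27.0 | 52.6 / 68.8 / 69.0 |
| 0.5 | 14.8 / 24.9 / 30.3 | 50.2 / 66.1 / 65.7 |

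Tests per 100 women are 65 / 91 / 96 at any correlation.

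**Gains in points (from unrounded values)**

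| Comparison | Both | At least one | Tests per 100 |
|---|---|---|---|
| Website v usual care | 9.3 / 9.9 / 10.1 | 16.7 / 16.1 / 15.9 | 26 |
| Call v website | 4.1 / 4.8 / 5.4 | 0.9 / 0.2 / -0.4 | 5 |

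(The three values are for correlation 0, 0.3 and 0.5.)

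**Can the order of the arms change?** Compared with usual care, the call has the lower ratio when its incremental cost, as a multiple of the website's, is below the ratio of the two gains.

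- Correlation 0, both: (22.4 - 9.0)/(18.3 - 9.0) = 13.4/9.3 = 1.44.
- Correlation 0, at least one: (73.6 - 56.0)/(72.7 - 56.0) = 17.6/16.7 = 1.05.

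So if the call costs 1.05 to 1.44 times the website, the two denominators order the arms differently. For example, take incremental costs of 10 and 12 units per woman. Per additional woman with both tests, the website costs 10/0.093 = 108 and the call 12/0.134 = 90. Per additional woman with at least one test, the website costs 10/0.167 = 60 and the call 12/0.176 = 68. At correlation 0.5 the call reaches slightly fewer women than the website on at least one. If it also costs more, it is dominated on that measure, while the both-tests ratio still shows a gain of 5.4 points.

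**Size of the half share.** Let s be the part of the incremental cost that is not directly tracked, and suppose that tracked time is carried in full. A single-test ratio then carries (1 - s) + s/2 = 1 - s/2 of the cost: 0.875 at s = 0.25, 0.75 at s = 0.5, and 0.5 only at s = 1. The protocol does not give s.

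**The case against.** The strongest reply is that nothing is missing. The Program Effectiveness paragraph lists three outcomes for Group B, the focus sentence can be read as the same list, and each item has its own equations. Section B.8 is background. This reading is tenable, so it cannot be stated as fact that the protocol's measure has no equation. The singular individual in the focus sentence and the wording in B.8 favor the at-least-one reading, but the text does not settle it. On the list reading it remains true that no Group B ratio sets the full cost against all the screening gained.

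Other replies also have force:

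- Completing both tests is a legitimate outcome; D.12 names it as the secondary outcome. Differences between cost per woman with both tests, per woman with at least one and per test are differences of unit, not bias.
- Apportioning by eligibility is a declared method with a cited precedent.
- At least one test scores two tests the same as one. For call v website its gain is near zero, so a ratio built on it alone would be unstable. With 250 Group B women per arm, the 95% half-width at correlation 0 is 1.96 × √(0.727 × 0.273/250 + 0.736 × 0.264/250) = 0.078, about 8 points. This is a reason to report it beside a per-test ratio, not alone.
- The planned sensitivity analysis covers methods uncertainty in general terms, so varying the one-half share would fit, but the share is not named.

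A reader might infer that the Group B CRC ratio shows half of what was spent. That holds only if all cost is shared, and the plan tracks participant and counselor time directly. A reader might also infer that CRC promotion is bound to look cheaper in Group B than in Group A. The printed Group A equations use percent with breast screening, although the text names CRC screening as that group's outcome. No Group A CRC ratio is therefore printed to compare with until the two are reconciled.

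**Conclusion.** The concern stands for Group B. The equations do not implement the measure that B.8 and the focus sentence state on their more natural reading. On either reading, the only full-cost ratio gives no credit for completing one needed test, and the single-test ratios leave out half of the shared cost by an eligibility rule.

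Under the assumed rates, call v website looks like a gain of 4.1 to 5.4 points on one denominator and of about nothing (-0.4 to +0.9) on the other. A reader might infer that the planned analysis will rank the arms wrongly. The documents do not support that: reversal is possible and not certain. It depends on arm costs and an association that are not given, on CRC rates stated for both groups combined, and on mammography rates from a different study. The combined arm is left out because no mammography rate is given for it.

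**What to change.** In D.13, Aim 2:

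1. State whether the focus sentence means at least one test or the three separate outcomes, and align B.8 with it.
2. Add two full-cost ratios for Group B beside the existing ones: per additional woman with at least one needed test, and per additional needed test completed (0, 1 or 2 per woman).
3. Name the primary Group B ratio before outcome data are seen.
4. Name the one-half share as an input to the sensitivity analysis, for example over 0.25 to 0.75.
5. Reconcile the Group A equations with the stated Group A outcome before any comparison between the groups. A ratio pooling Groups A and B is optional; it would reflect the 30/70 enrollment ratio.

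This needs only analysis-plan wording and a few more ratios from data already being collected. The cost is more ratios to report and a commitment to one of them in advance.
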